## 7.1 Primary Criterion

The primary criterion (off-site read) is calculated by subject, and by independent blinded reader in a centralized procedure (off-site readers), in averaging the Contrast to Noise Ratio (CNR) for maximum 3 enhanced lesions. Only lesions detected by both MRIs after lesion tracking will be used. The evaluation will be done on combined images sets (1a, 2) and (1b, 3).

CNR is a variable derived for each lesion, from the Signal Intensity (SI) measurement. CNR will be calculated according to the following formula:

$$CNR = \frac{SI_{lesion} - SI_{ht}}{SD_{noise}}$$

where,

$SI_{lesion}$  = the SI in the Region Of Interest (ROI) in the lesion

$SI_{ht}$  = the SI in the ROI in healthy tissue (brain or spinal cord)

$SD_{noise}$  = standard deviation of background noise.

The SI measurement will be performed by the independent blinded readers on the pre and post-injection, axial 3D T1 weighted Gradient Echo (GRE) for brain and sagittal T1-weighted Spin-Echo (SE) or Turbo Spin-Echo (TSE) for spine, sequences. The post CNR value will be normalized by the pre-CNR (baseline) value.

Measurements of the SI of the lesion are to be made on the best representative images of the pathology, along with the SI of normal brain (white or gray matter) or spinal cord tissue, and of the image background.

 CONFIDENTIAL	Protocol No. GDX-44-004 Version No. 2.0 (Protocol including amendment n°1) Date: 11 July , 2016	 Page 35 / 84
---------------------------------------------------------------------------------------------------	----------------------------------------------------------------------------------------------------------	-----------------------------------------------------------------------------------------------------

These images will be selected according to the following:

- Up to 3 most representative lesions (largest enhancing lesion) will be measured separately.
- The lesion must have a size of at least 5 mm (long axis) to avoid partial volume averaging.
- The ROI for a lesion will encompass a homogeneous area within the lesion as large as possible.

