#### Primary analysis of the primary criterion

The primary objective of the study is to determine a safe and effective dose of P03277 based on a comparison of Contrast to Noise Ratio (CNR) between several doses, 0.025, 0.05, 0.1, 0.2 mmol/kg, of P03277 and MultiHance® at 0.1 mmol/kg.

The primary criterion is the Contrast to Noise Ratio (CNR) calculated from the Signal Intensity (SI) measurement of maximum 3 enhanced lesions by the 3 independent blinded readers (see [section 7.1](#))

The primary analysis will test differences of means of primary criterion for each dose of P03277 compared to MultiHance® and will be done for each of the 3 independent blinded readers (off-site) using the PPS. Holm's step-down method will be used to address multiplicity testing considering the 4 treatment groups to be tested.

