#### Secondary analyses of the primary criterion

- **FAS analysis**
  - The primary analysis will be repeated using the FAS.
- **Overall analysis**
  - The primary analysis will be repeated by pooling together all off-site readers using the FAS and the PPS.
- **Centre Effect**
  - By-site summaries will be produced to look for potential disparities among the sites (center effect) using the FAS and the PPS. The p-values will not be reported for the by-site summaries.
- **Dose/response evaluation**
  - The relationship between doses of P03277 and response will be evaluated graphically based on mean profile during the study using the FAS and the PPS.
  - Depending on the graphical results, a more complex model including doses of P03277 (as continuous variable) could be fitted to evaluate the relationship between doses and CNR increase.

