### 3. STATISTICAL METHODS

### 3.1. General considerations

After the database lock, the statistical analysis will be performed by Inferential under the supervision of [name], Guerbet biostatistician, on the basis of the present document. A quality control of the statistical analysis will be performed to ensure the reliability of the results.

Thorough description of all parameters reported will be presented separately by group. Summary tabulated results will be provided by group and assessment time, if relevant or they will be replaced by the corresponding individual data listings if too few subjects are concerned.

Tabulations of quantitative parameters will include the following summary statistics: number of subjects, mean, SD, minimum, median and maximum. If for a given parameter, the raw value has been collected with  $x$  decimal places, the mean, median and SD will be rounded to  $x+1$  decimal places, while the minimum and maximum values will be tabulated as reported with  $x$  decimal places.

Tabulations of frequencies for categorical data will include all possible categories and will display the number of observations in a category as well as the percentage (%) relative to the respective group. Percentages will be rounded to one decimal place. The category missing will be displayed only if there are actually missing values. Percentages will be calculated on the total of non-missing recorded categories.

For safety analyses, the baseline value will be defined as the last available value prior to administration of the Investigational Medicinal Product (IMP). For the primary analysis of the primary efficacy criterion, the baseline value will be the pre CNR measurement for unenhanced lesions for each contrast agent period.

All statistical tests will be performed at the significant threshold of 2.5% one-sided. P-values will be displayed with 4 decimal places.

SAS® version 9.2 will be used for all descriptive summaries and inferential analyses.

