### 3.3. Determination of sample size

Based on the hypothesis below, a total of 280 subjects were to be enrolled in the study:

- Subset 1: maximum 40 subjects (depending of the number of participating sites) on the basis of 1 subject per site.
- Subset 2: minimum 240 subjects based on the following assumption: the study aims at detecting a minimum of 30% increase of CNR for at least one of the four tested dose of P03277 compared to control arm MultiHance® at dose of 0.1 mmol/kg BW. A sample size of 50 evaluable subjects per group was required to obtain a power of at least 90%, using a t-test of a normal mean difference with a one-sided significance level of 0.025 (Holm's step-down method in a multiple comparisons design [1]) and a common SD of 3.01. Therefore, a minimum of 50 evaluable subjects per dose group and a minimum of 200 evaluable subjects in total would have to be enrolled in this study.

An evaluable subject was defined as a randomized subject, 2 contrast agents administered, having undergone 2 complete, assessable and interpretable MRI examinations, presenting with at least one enhancing lesion of minimum 5 mm (long axis).

It was anticipated that some of the subjects would not complete both MRI evaluations. To offset this, an additional 10 subjects per group were added to the 50 required leading to a total of 240 randomized subjects.

The number of non-evaluable subjects was monitored to assess the necessity for a sample size increase. The decision to increase the sample size would be made by the sponsor when approximately 80% of the planned 240 randomized subjects were enrolled. The actual rate of drop-out subjects was considered to assess the new number of subjects to be enrolled.

Subjects with brain metastasis were randomized at a minimum of 20% of the second subset of subjects. Randomization was stratified within brain metastasis (yes/no) in order to prevent unequal contrast agent allocation.

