### 5.5.2. Supportive analyses of primary criterion

### 5.5.2.1 FAS Analysis

The primary analysis will be repeated using the FAS. However, this analysis will be restricted to subjects with CNR data at both MRIs. It will avoid the mixed model to impute any missing CNR data. All lesions will be considered, including not matched lesions, on the contrary to the primary analysis. Lesions not matching between both MRIs will therefore be included in this supportive analysis.

The table and the figure that will be displayed are detailed in Section 6.1.2.1.2.

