### 5.5.2.2 Overall Analysis

The primary analysis will be repeated using the PPS for matching lesions only and considering in the same model data from the 3 off-site readers. The reader factor will be included in the model and repeated by subject.

For each dose of P03277 SAS® procedure used for this analysis will be the following:

```

proc mixed data = XXX method = REML;
  class subject trt period reader;
  model eval = trt period baseline reader trt*reader;
  random subject / type = cs;
  lsmeans trt / pdiff = controlu('MultiHance') tdiff cl alpha = 0.025;
  lsmeans trt;
  estimate "P03277 - MultiHance" trt 1 -1 /cl;
run;

```

The table that will be displayed is detailed in Section 6.1.2.1.2.

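### The SAP's FAS repeat of the primary analysis changes subjects and lesions together, so no planned comparison with MultiHance isolates the effect of the PPS exclusions

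*SAP*

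**What the plan says.** **Protocol.** Section 7.1 limits the criterion to matched lesions: "Only lesions detected by both MRIs after lesion tracking will be used". It makes no exception by analysis set. In Section 12.3 the primary analysis is done for each of the three "independent blinded readers (off-site) using the PPS". Under the secondary analyses of the primary criterion, the same section states: "The primary analysis will be repeated using the FAS". It plans the pooled-reader analysis on both FAS and PPS. Read together, these passages describe a FAS repeat on matched lesions.

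**SAP.** Section 2.2.1 attaches the matching rule to the primary analysis only. Section 5.5.2.1 repeats that analysis on FAS subjects with CNR at both MRIs, but: "All lesions will be considered, including not matched lesions, on the contrary to the primary analysis". It gives a reason for requiring both MRIs and none for admitting unmatched lesions. For the pooled readers, Section 5.5.2.2 says: "The primary analysis will be repeated using the PPS for matching lesions only". The FAS version planned in the protocol is gone. Section 4, which explains departures from the planned analyses, covers the reduced PPS repeat of secondary criteria and three added criteria. It mentions neither of these changes.

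**The concern.** The superiority test rests on a set from which subjects are removed for major deviations. Several of these arise after randomisation. SAP 5.2.2 lists, among others, an administered volume more than 20% off target, extravasation, more than 21 days between MRIs, an intervening treatment affecting lesion size, and loss of blinding at central reading. The final split into major and non-major is still to be made before the blind is broken. A FAS repeat is the usual check that such exclusions do not drive the result.

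That check works only if the analysis set is the one thing that changes. Here the lesion rule changes too, and the two examinations of one subject may then be averaged over different lesions. The FAS repeat will also carry its own test (SAP 3.1: "All statistical tests will be performed at the significant threshold of 2.5% one-sided"), so readers will set it beside the primary result.

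**Working it through.** **1. Does any planned comparison change the set alone?**

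| Analysis | Subjects | Lesions | MultiHance contrast |
|---|---|---|---|
| Primary (SAP 5.5.1) | PPS | matched | yes |
| FAS repeat (5.5.2.1) | FAS, both MRIs | all | yes |
| Pooled readers (5.5.2.2) | PPS | matched | yes |
| Descriptive CNR (5.5.2.3) | FAS, both MRIs; overall tables also on PPS | PPS tables matched only | descriptive |
| Similar ROI placement (5.5.2.4) | PPS | matched | yes |
| Dose-response (5.5.3.1) | FAS with P03277 data | not restricted in the text | none |
| Three added criteria (5.5.4) | FAS and PPS | PPS matched only | yes |

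No row pairs the FAS with matched lesions in a comparison with MultiHance.

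**2. The plan's own figure.** SAP 3.3 states: "A sample size of 50 evaluable subjects per group was required to obtain a power of at least 90" per cent, for "detecting a minimum of 30% increase of CNR" with a common SD of 3.01. The mean CNR under MultiHance is not given, so the 50 cannot be reproduced directly. Solving backwards with the normal approximation:

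- Two samples, one-sided alpha 0.025: 3.01 × (1.960 + 1.2816) × √(2/50) = 1.95, so the reference mean is 1.95/0.30 = 6.5.
- Paired, with 3.01 as the SD of differences: 3.01 × 3.2415 × √(1/50) = 1.38, reference 4.6.
- At the first Holm step, 0.025/4: 2.28 (reference 7.6) for two samples, or 1.61 (reference 5.4) paired.

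The documents do not say which applies, so 50 is neither confirmed nor refuted. Nothing in this point changes the sample size.

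**3. What an unmatched lesion does in the all-lesion run.** The subject's value is a mean over at most three lesions, the largest enhancing ones, each at least 5 mm (Protocol 7.1). Adding one lesion of CNR c to k measured lesions with mean m changes that mean by (c − m)/(k + 1), provided k is below three.

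Assumed values: MultiHance 10, P03277 13 (the planned +30%), and an extra lesion of CNR 4 seen only with P03277.

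- k = 1: (13 + 4)/2 = 8.5, and 8.5 − 10 = −1.5 instead of +3.0.
- k = 2: (13 + 13 + 4)/3 = 10, and 10 − 10 = 0.
- Three larger matched lesions: the cap is full and the gain stays +3.0.
- Brighter extra lesion, CNR 20, k = 1: (13 + 20)/2 = 16.5, a gain of +6.5.

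If a fraction f of subjects has the extra lesion of CNR 4, the mean gain is 3.0 − 4.5f for k = 1 and 3.0 − 3.0f for k = 2:

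| f | one matched lesion | two matched lesions |
|---|---|---|
| 10% | 2.55 | 2.7 |
| 20% | 2.10 | 2.4 |
| 30% | 1.65 | 2.1 |

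**4. The same without a reference mean.** The assumed 10 lies above the 4.6 to 7.6 found in step 2, so a relative form is safer. Let r = c/m. The apparent gain is 1.3 × [1 − f(1 − r)/(k + 1)] − 1. For r from 0.3 to 0.7 and f from 10% to 30%, a true 30% gain appears as about 16% to 28% with one matched lesion and 21% to 29% with two.

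Steps 3 and 4 ignore the pre-contrast CNR covariate, which may offset part of the shift.

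**The case against.** Dropping the matching rule is a defensible sensitivity analysis. Matching is determined after contrast, so conditioning on it is itself a selection. The comparison is within subject, so exclusions do not unbalance P03277 against MultiHance as they would in a parallel-arm trial. Major deviations are tabulated by contrast agent. The list of tables in SAP Section 6 is not visible in the public copy, so a further table cannot be ruled out. All of this stands. It supports keeping the all-lesion run, but it does not supply the missing comparison, and the text of SAP 5.5.2 describes only one FAS repeat.

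Four stronger readings are tempting, and the documents do not support them.

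- A reader might infer that the superiority test penalises an agent that reveals an extra lesion. It does not: that test, the pooled-reader model and the ROI analysis all use matched lesions only. A downward shift for P03277 in the FAS run would make that run conservative and could not create false superiority.
- A reader might infer that the all-lesion mean is always biased against the more sensitive agent. The direction depends on brightness and the three-lesion cap. It could also reverse at doses where MultiHance shows more, and Protocol 10.1.2 expects some doses to have lesser efficacy.
- A reader might infer that the exclusions are never examined. Excluded subjects with CNR at both MRIs do re-enter the FAS run; their effect is confounded with the lesion rule, not absent.
- A reader might infer that the PPS is the wrong primary set. Protocol and SAP agree on it in advance. Preferring the FAS is a matter of judgement, and this point does not need it.

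**Conclusion.** The concern holds as a gap in the supportive analyses and an unrecorded departure from the protocol. From the SAP text, no planned comparison with MultiHance changes the analysis set while holding the lesion rule fixed, so neither agreement nor disagreement between PPS and FAS can be attributed to the exclusions.

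The distortion within the all-lesion run could be material: an assumed mean gain of 3.0 becomes 2.55 to 1.65 with one matched lesion, or 2.7 to 2.1 with two, if 10% to 30% of subjects are affected. These figures rest on assumed CNRs, an extra lesion that is duller than the subject's mean and seen only with P03277, and no covariate offset. The documents give neither the share of unmatched lesions nor the expected PPS exclusion rate, so the actual size and sign are unknown. The primary Holm test is unaffected.

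**What to change.** - Add a FAS analysis on matched lesions: FAS subjects with matched-lesion CNR at both MRIs, analysed by allocated agent with the primary model. Run it per reader and pooled, and report it beside the PPS result.
- Keep the all-lesion FAS run as a separately labelled sensitivity analysis, with its purpose stated. Its difference from the new run then reflects the lesion rule, together with any subjects who have no matched lesion.
- Record in SAP Section 4 the change of lesion rule and the change to the pooled-reader analysis, with reasons.
- State that subjects with no matched lesion or a missing MRI remain outside the matched-lesion FAS run, so it checks only the recoverable exclusions.

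The PPS remains the prespecified primary set. The cost is a rerun of existing code (3 readers × 4 doses = 12 models, plus 4 pooled models, one per dose) and some SAP wording, with no new data. It is best settled before the blind is broken.

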### 5.5.2.2 Overall Analysis

The primary analysis will be repeated using the PPS for matching lesions only and considering in the same model data from the 3 off-site readers. The reader factor will be included in the model and repeated by subject.

For each dose of P03277 SAS® procedure used for this analysis will be the following:

```

proc mixed data = XXX method = REML;
  class subject trt period reader;
  model eval = trt period baseline reader trt*reader;
  random subject / type = cs;
  lsmeans trt / pdiff = controlu('MultiHance') tdiff cl alpha = 0.025;
  lsmeans trt;
  estimate "P03277 - MultiHance" trt 1 -1 /cl;
run;

```

The table that will be displayed is detailed in Section 6.1.2.1.2.

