## 9.2 Imaging Protocol

### 9.2.1 *MR equipment*

The procedure will be performed using a MRI scanner that can perform the required pulse sequences with a dedicated head coil or a spine coil. MRI units with 1.5T or 3T magnetic field will be used, regardless of the manufacturer. The following information must be recorded: the manufacturer, model, software version, and field strength of the MRI device.

For a single subject, it is mandatory to use the same MR equipment for the two MRI examinations required by the protocol.

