#### 9.4.9 *Lesion tracking (not applicable for global matched-pairs reads)*

All 3 blinded readers will independently identify the location of all the lesion(s) detected in the image sets. The location for each lesion will be marked along with a number in ascending order on a CNS diagram 

To allow exact matching of lesions throughout the different imaging sequences examinations, an independent radiologist (lesion tracker) will perform the ‘lesion tracking’ based only on the available CNS diagrams for a given subject. All CNS diagrams for each subject will be displayed simultaneously.

 CONFIDENTIAL	Protocol No. GDX-44-004 Version No. 2.0 (Protocol including amendment n°1) Date: 11 July, 2016	 Page 50 / 84
---------------------------------------------------------------------------------------------------	---------------------------------------------------------------------------------------------------------	-----------------------------------------------------------------------------------------------------

Because a unique numbering of the lesions cannot be ensured during the blinded image evaluations by 3 readers, the lesion tracker will assign a new number for each lesion to be tracked, which will then be matched and correlated to the numbers indicated on the CNS diagrams.

The independent lesion tracker will not obtain any information about the contrast medium used for the enhanced MRI.

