## STATISTICAL ANALYSIS PLAN N° GDX-44-004

VERSION 1.0

DATED: 09JAN2018

Page 23 / 60

	Central Laboratory Biochemistry results not available	Laboratory data base	Non major
	Central Laboratory Hematology results not available	Laboratory data base	Non major
	Urinalysis not performed	Clinical data base	Non major
	Vital signs not measured	Clinical data base	Non major
	Vital sign result missing	Clinical data base	Non major
	ECG not performed/Performed but not in triplicate	Clinical data base	Non major
	ECG result missing	Central ECG data base	Non major
	Tolerance at injection site is not filled in for patient receiving the study product	Clinical data base	Non major
	No VAS completed in case of injection site pain	Clinical data base	Non major
Non respect of study's schedule and procedures	MRI examination not performed	Clinical data base	Major
	Time between the two MRI procedures is strictly greater than 14 days and less or equal to 21 days	Clinical data base	Non major
	Time between the two MRI procedures is strictly greater than 21 days	Clinical data base	Major
	Time between contrast media administration and 3-D GRE acquisition for Brain and T1WSE/TSE acquisition for spine is greater than 10 minutes	Clinical data base	Non major
	Two different MRI system manufacturer used for both assessments	Imaging data base	Non major
	Two different MRI system model used for both assessments	Imaging data base	Non major
	Two different MRI system software version used for both assessments	Imaging data base	Non major
	Two different magnetic field strength used for both assessments	Imaging data base	Non major
	Two different MRI machines used for both assessments	Monitoring	Non major
	MRI machine used not qualified	Monitoring	Non major
	MRI exam for subject of subset 2 performed prior investigator's qualification	Monitoring	Non major
	Time between contrast media administration and 3-D GRE acquisition for Brain and T1WSE/TSE for spine acquisition is different of more than 10 minutes but less than 30 minutes between the two MRI for a single patient	Clinical data base	Non major
	Time between contrast media administration and 3-D GRE acquisition for Brain and T1WSE/TSE for spine acquisition is different of more than 30 minutes between the two MRI for a single patient	Clinical data base	Major
	Time between screening visit and first contrast media administration is strictly greater than 7 days	Clinical data base	Non major

CONFIDENTIAL

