## STATISTICAL ANALYSIS PLAN N° GDX-44-004

Page 24 / 60

VERSION 1.0

DATED: 09JAN2018

[REDACTED]

	Prior to MRI blood sample for central laboratory assessment is not drawn before contrast media administration	Clinical data base	Non major
	Prior to MRI urinalysis is not performed before contrast media administration	Clinical data base	Non major
	1 day post MRI blood sample for central laboratory assessment is not drawn the day after contrast media administration	Clinical data base	Non major
	1 day post MRI urinalysis is not performed the day after contrast media administration	Clinical data base	Non major
	Before injection vital sign is not taken before contrast media administration	Clinical data base	Non major
	45-minute after injection vital sign is not taken between 30 and 60 minutes after contrast media administration	Clinical data base	Non major
	Between 2 and 4 hours after injection vital sign is not taken between 2 and 4 hours after contrast media administration	Clinical data base	Non major
	1 day post MRI vital sign is not taken the day after contrast media administration	Clinical data base	Non major
	Before injection ECG is not performed before contrast media administration	Clinical data base	Non major
	45-minute after injection ECG is not performed between 30 and 60 minutes after contrast media administration	Clinical data base	Non major
	Between 2 and 4 hours after injection ECG is not performed between 2 and 4 hours after contrast media administration	Clinical data base	Non major
	1 day post MRI ECG is not performed the day after contrast media administration	Clinical data base	Non major
GCP deviation	ICF deviation	Monitoring	Non major
	Source document management not appropriate	Monitoring	Non major

Subjects presenting at least one protocol deviation with a status major will be excluded from the PPS.

Frequency and percentages of subjects with protocol deviations will be presented breaking down by status (major/non major).

Subjects with major protocol deviations throughout the study causing exclusion from the PPS will be presented by contrast agent and globally on the Extended Set for each subset separately: subjects with at least one major protocol deviation and subjects with each major protocol deviation. Non major protocol deviations will follow the same disposition.

The tables and listings that will be displayed are detailed in Sections 6.1.1.2 and 6.2.2.

CONFIDENTIAL	FORM	
STATISTICAL ANALYSIS PLAN N° GDX-44-004		Page 25 / 60

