### 5.5.1. Primary analysis of the primary criteria

The primary objective of the study is to determine a safe and effective dose of P03277 based on a comparison of CNR between several doses, 0.025, 0.05, 0.1 and 0.2 mmol/kg of P03277 and MultiHance® at 0.1 mmol/kg.

The primary criterion is the CNR calculated from the SI measurement of maximum 3 enhanced lesions by the 3 independent blinded readers. CNR averaged for matching lesions per subject will be used in the primary analysis.

The primary analysis will test differences of means of primary criterion for each dose of P03277 compared to MultiHance® and will be done for each of the 3 independent blinded readers (off-site) using the PPS. Holm's step-down method [1] will be used to address multiplicity testing considering the 4 contrast agents to be tested.

A subject will be analyzed as soon as he has a matching evaluation of the CNR at both MRIs by at least one off-site reader. Therefore the numbers of subjects analyzed by reader may be different.

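### The supportive pooled-reader model in SAP 5.5.2.2 leaves out subject-by-exam and subject-by-reader variance, so its standard error is right only at one particular variance ratio

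*SAP*

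**What the plan says.** SAP 5.5.2.2 (Overall Analysis) reruns the primary analysis on the PPS, matched lesions only, with the data of all three off-site readers in one model for each P03277 dose. On the structure it says: "The reader factor will be included in the model and repeated by subject". The code has treatment, period, baseline, reader and treatment-by-reader as fixed effects, and one covariance line, "random subject / type = cs". It contains no subject-by-treatment term, no subject-by-reader term and no REPEATED statement.

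Other parts of the plan bear on how a subject's six values are related:

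- Protocol 9.4.9: "All 3 blinded readers will independently identify the location of all the lesion(s) detected in the image sets".
- Protocol 9.2.1: "For a single subject, it is mandatory to use the same MR equipment for the two MRI examinations required by the protocol".
- The deviation table in SAP 5.2.2 lists "Two different magnetic field strength used for both assessments" and grades it non-major. The exclusion rule there is "Subjects presenting at least one protocol deviation with a status major will be excluded from the PPS", so such subjects stay in the set that the pooled model uses.
- SAP 3.1, for the primary analysis: "the baseline value will be the pre CNR measurement for unenhanced lesions for each contrast agent period".
- SAP 5.5.1, on readers: "Therefore the numbers of subjects analyzed by reader may be different".

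**The concern.** Six CNR values from one subject can share variation in three ways: through the subject, through the exam (one scan, read three times) and through the reader (one reader, two scans). The printed model allows only the first. Anything that moves all three reads of one scan together, such as scanner state or slice position, goes straight into the P03277 versus MultiHance difference and belongs in its error. Variation between readers within a subject cancels from that difference and should stay out of its error. The printed model mixes both into a single residual.

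At stake is one supportive result per dose: a pooled difference, a 95% interval and a one-sided p-value. No decision rule uses them. But SAP 5.5.1.5 weighs the doses on overall benefit and risk, and allows a dose not shown superior on CNR to be recommended. A pooled CNR interval may then be read closely, and a reader of the report could not tell whether it is too narrow or too wide.

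**Working it through.** **Inputs.** From the SAP: 3 readers, 2 exams per subject, the model in 5.5.2.2, one-sided 2.5% (3.1) and 50 evaluable subjects per dose (3.3). The SAP states no figure for the pooled model, so there is none to reproduce. The variance components sST, sSR and sE are not given and are assumed over a range.

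**True variance.** Take a CNR value as fixed effects + subject + subject-by-exam (sST) + subject-by-reader (sSR) + residual (sE). Each subject receives each agent once, so subject-by-exam and subject-by-treatment are the same term. Average one subject's difference between agents over the three readers. The subject and subject-by-reader terms cancel, which leaves variance 2sST + 2sE/3. Over n subjects:

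Var(true) = (2/3n)(sE + 3sST).

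**Variance the printed model reports.** The five within-subject degrees of freedom have these expected mean squares:

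- exam, 1 df: sE + 3sST
- reader, 2 df: sE + 2sSR
- exam by reader, 2 df: sE

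With a subject intercept alone, all five are pooled: [(sE + 3sST) + 2(sE + 2sSR) + 2sE]/5 = sE + 0.6sST + 0.8sSR. Hence:

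Var(model) = (2/3n)(sE + 0.6sST + 0.8sSR).

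**Where they agree.** Equality needs 2.4sST = 0.8sSR, that is sSR = 3sST, which includes both being zero. If sSR is smaller, the reported SE is too small; if larger, it is too large.

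**Numbers for sST = sE = 1.** The true factor is 1 + 3 = 4.

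- sSR = 1: model factor 1 + 0.6 + 0.8 = 2.4. True SE/model SE = sqrt(4/2.4) = 1.29. One-sided error = P(Z > 1.96/1.29) = 6.4%.
- sSR = 3: model factor 1 + 0.6 + 2.4 = 4. Ratio 1, error 2.5%.
- sSR = 6: model factor 1 + 0.6 + 4.8 = 6.4. SE ratio sqrt(4/6.4) = 0.79, error 0.7%.

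The same formula over a wider range gives these one-sided errors (nominal 2.5%):

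| sST/sE (assumed) | sSR = 0 | sSR = sST | sSR = 3sST | sSR = 6sST |
|---|---|---|---|---|
| 1/9 | 4.0% | 3.4% | 2.5% | 1.6% |
| 1/3 | 6.4% | 4.7% | 2.5% | 1.0% |
| 1 | 10.8% | 6.4% | 2.5% | 0.7% |
| 4 | 15.8% | 8.1% | 2.5% | 0.5% |

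**Simulation with the full fixed effects.** REML fits with period, exam-specific baseline, reader and treatment-by-reader, 50 subjects and sST = sE. There were 2,000 runs per setting (1,500 for sSR = 0); the Monte Carlo standard error is about 0.35 points at 2.5%. Each cell shows the printed model, then the model with subject-by-treatment and subject-by-reader terms tested on subjects minus 2 df.

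| sSR | complete data | 15% of subject-reader pairs missing (assumed) |
|---|---|---|
| 0 | 10.9%, 2.3% | 9.3%, 1.9% |
| sST | 6.7%, 2.5% | 6.0%, 2.6% |
| 3sST | 2.9%, 2.9% | 2.0%, 2.2% |
| 6sST | 0.9%, 2.7% | 0.8%, 2.4% |

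The formula holds closely with baseline and period in the model, and the fault persists when reader counts differ. Across all 14 settings simulated, the extended model gave 1.9 to 3.2%.

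**The case against.** The strongest reply is that nothing in the documents says which way the error goes. Readers who locate lesions independently raise sSR. The same-equipment rule limits sST, and the exam-specific baseline may absorb part of what remains. All three push away from a standard error that is too small. Different scanners or field strengths are only listed as possible deviations, with no frequency. This stands: the error rates above illustrate the mechanism and do not estimate its size in this trial. It does not rescue the printed model, because nothing in the documents supports the one ratio at which that model is right, and the extended model needs no guess.

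A second reply is also sound. The missing REPEATED statement is not itself the defect. A subject intercept gives the same marginal model as a compound-symmetry REPEATED statement when the correlation is non-negative, so clustering by subject is handled. What is missing is the exam-level and reader-level structure.

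A reader might also infer from the ESTIMATE lines (5.5.1.3, 5.5.2.2, 5.5.4.5, 5.5.4.6) that the reported difference has the wrong sign. The documents do not show this. The dataset is a placeholder and the coding of the test agent is not given. The sign would reverse only if MultiHance is the first treatment level: under alphabetical ordering, itself an assumption, it sorts before a level named P03277 0.1 mmol/kg but after one named 0.1 mmol/kg. The LSMEANS line in the same block names its control, so a reversed ESTIMATE would disagree visibly with it.

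**Conclusion.** The pooled model in SAP 5.5.2.2 is wrong as written: its SE, interval and p-value are valid only if sSR = 3sST. The condition is exact for complete data without the baseline covariate, and simulation with baseline and period agrees closely. Direction and size cannot be determined from the documents.

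Two stronger readings are not supported. One is that the pooled interval is too narrow; it may equally be too wide. The other is that the primary analysis is affected. The per-reader models have two values per subject, for which a subject intercept is sufficient. Neither the Holm procedure nor the rule in Protocol 12.3 requiring two of three readers uses the pooled model. This should be corrected before the analysis is run, but it does not threaten the trial's main conclusion.

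**What to change.** In SAP 5.5.2.2:

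1. Replace the RANDOM line with `random subject subject*trt subject*reader;`.
2. State the denominator-df method, chosen so that the treatment contrast is tested on about subjects minus 2 df. The simulation imposed that value; a software default may not deliver it.
3. Reword the sentence on reader being repeated by subject so that it describes these three random terms.

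The cost is one line of code, the df option and one sentence, with no new data. Error df per dose fall from about 243 (300 values, less 8 fixed-effect parameters and 49 for subjects) to about 48. Intervals may move either way. In simulation with sST = sE, scaled so that sST + sE = 1, the reported SE goes from 0.128 to 0.167 if sSR = sST, and from 0.209 to 0.165 if sSR = 6sST.

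Programming note only, not an error shown in the plan: when coding, fix the treatment level order so that `trt 1 -1` in the four ESTIMATE lines matches its label of P03277 minus MultiHance.
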